10.6.1.1. Pharmacokinetic Samples

Pharmacokinetic samples will be disposed of after the Bioanalytical Report finalization or 6 months after issuance of the draft Bioanalytical Report (whichever is earlier), unless requested for future analyses.

Pharmacokinetic samples may be disposed of or anonymized by pooling. Additional analyses may be conducted on the anonymized, pooled PK samples to further evaluate and validate the analytical method. Any results from such analyses may be reported separately from the CSR.

Incurred sample reproducibility analysis, if any, will be performed alongside the bioanalysis of the test samples. The results from the evaluation will not be reported in the CSR but separately in a Bioanalytical Report.

10.6.1.2. Pharmacodynamic Samples – Not Applicable

10.6.1.3. Pharmacogenetic Samples – Not Applicable

10.6.2. Labeling and Shipment of Biohazard Samples

Samples will be labeled and shipped in accordance with the Laboratory Manual and the Biological Substance, Category B regulations (materials containing or suspected to contain infectious substances that do not meet Category A criteria), see [Appendix B](#), 'IATA 6.2 Guidance Document'.

Any samples identified as Infectious Category A materials will not be shipped and no further samples will be taken from the subject unless agreed with AstraZeneca and appropriate labeling, shipment and containment provisions are approved.

10.6.3. Chain of Custody of Biological Samples

A full chain of custody will be maintained for all samples throughout their lifecycle.

The Investigator will ensure full traceability of collected biological samples from the subjects while in storage at the study centre until shipment and will keep documentation of receipt of arrival.

The sample receiver will keep full traceability of samples while in storage and during use, until used, disposed of, or until further shipment or disposal (where appropriate) and will keep documentation of receipt of arrival.

Samples retained for further use will be registered in the AstraZeneca biobank system during the entire life cycle.

10.6.4. Withdrawal of Informed Consent for Donated Biological Samples

If a subject withdraws consent to the use of donated biological samples, the samples will be disposed if not already analysed and the action documented.

As collection of donated biological samples is an integral part of the study, the subject is then withdrawn from further study participation. If the subject withdraws consent for the genetic component of the study, then they may continue in the study.

AstraZeneca ensures the central laboratory(ies) holding the samples is/are informed about the withdrawn consent immediately and that samples are disposed of/destroyed, the action documented, and the signed document returned to the study centre.

11. DATA QUALITY ASSURANCE AND DATA MANAGEMENT

11.1. Quality Control and Source Data Verification

Source data verification will be conducted with due regard to subject confidentiality.

The study centre will allow the study monitor and Sponsor representative direct access to all study documents, medical files and source documents to enable verification of the study data, while maintaining the anonymity of the subject and confidentiality of the data.

Internal quality control will be performed at all stages of the study by the study centre.

11.2. Audit/Inspections

The study centre facilities and all study data/documentation may be audited/inspected by independent auditor/inspector/any representatives of regulatory authorities. The Investigator must allow the applicable persons access to all relevant facilities and data/documents. The Investigator must be available to discuss any findings/issues.

If an audit was performed, the audit certificate will be included in the CSR.

11.3. Study Monitoring

The conduct of the study will be monitored by an independent Parexel monitor or a subcontracted monitor to ensure compliance with applicable regulatory requirements and GCP. The summary of the documentation of the monitoring visits will form part of the study documentation and will be archived as such.

Monitoring visits at site will be limited to a minimum, required as deemed appropriate during COVID-19 pandemic.

11.4. Data Collection

The ClinBase™ system is an electronic source data capturing and information management system. The system combines all aspects of source data capturing with process control and clinical study management. All clinical and laboratory data, except those which are paper-based or provided by external vendor, will be collected in ClinBase™. Only paper-based data will be subject to data entry. For electronic source data, no data entry will be performed.

The responsible study monitor will check data at the monitoring visits to the study centre. The Investigator will ensure that the data collected are accurate, complete and legible. Data will be monitored within ClinBase™ by the study monitor before being exported. Any changes made during monitoring will be documented with a full audit trail within ClinBase™.

11.4.1. Case Report Forms and Source Documents

All data obtained using paper collection methods during the clinical study will be recorded in ClinBase™. All source documents from which ClinBase™ entries are derived should be placed in the subject's personal records.

The original ClinBase™ entries for each subject will be checked against source documents by the study monitor. Instances of missing or uninterpretable data will be discussed with the Investigator for resolution.

11.4.2. Access to Source Documents

During the course of the clinical study, a study monitor will make study centre visits to review protocol compliance, compare ClinBase™ entries and individual subject's personal records, assess IMP accountability and ensure that the clinical study is being conducted according to pertinent regulatory requirements. ClinBase™ entries will be verified against source documents. The review of medical records will be handled confidentially to ensure subject anonymity.

Checking of the ClinBase™ entries for completeness and clarity and verifying with source documents, will be required to monitor the clinical study for compliance with GCP and other regulations. Moreover, regulatory authorities of certain countries, IECs/Institutional Review Boards (IRB)s may wish to carry out source data inspections on-site, and the Sponsor's clinical quality assurance group may wish to carry out audits. Direct access to source data will be required for these inspections and audits; they will be carried out giving due consideration to data protection and subject confidentiality. The Investigator assures the Sponsor of the necessary support at all times.

11.5. Data Management

Parexel will utilize standardised and validated procedures and systems to collect, process and file the clinical data of this study. Any system used will be compliant with FDA 21 Code of Federal Regulations Part 11 requirements.

A data management plan (DMP) will be prepared to describe the processes and data-flow within the clinical study. Timelines, versions for the computer systems and the coding will be defined in the DMP, and if applicable, Sponsor-specific requests will also be documented within. The DMP will be finalized before first dose where possible but before database lock.

A data validation specification (DVS) will be created to outline the validation checks to be performed during the study. The DVS must be finalized before data validation.

After the data has been monitored by the responsible study monitor all data received will be reviewed, logged and filed.

The raw data intended for further processing will be checked by standard routines or according to the DVS and queries will be generated and sent to the Investigator for review

and resolution. Corrections resulting from these queries will be confirmed on the data clarification forms (DCFs). This process will be repeated until no further discrepancies are found. The data will then be declared as clean. Applicable documentation will be stored in the study files.

Only trained study staff will have access to the clinical database and every change in data will have a full audit trail.

12. STATISTICAL METHODS

12.1. Overview

The statistical methodology below describes the statistical analysis as it is foreseen when the study is being planned.

If circumstances should arise during the study rendering the analysis inappropriate, or if in the meantime improved methods of analysis should come to light, different analyses may be performed. A separate concentration-QT (C-QT) analysis plan for the primary C-QT analysis will be written for the study. A brief description of the primary analysis is provided in Section 12.9. All other analyses are described within this protocol. Any deviations from the statistical methodology defined in this protocol, reasons for such deviations and all alternative/additional statistical analyses that may be performed will be described in the CSR. Such changes to analyses may be written into an abbreviated statistical analysis plan, if appropriate. The verification and review of all statistical modeling assumptions will be documented appropriately.

12.2. General Statistical Methodology

All original and derived parameters as well as demographic and disposition data will be listed and described using summary statistics. All safety data (scheduled and unscheduled) will be presented in the data listings.

Demographic and baseline data will be summarised for all randomised subjects. Pharmacokinetic data will be summarised by treatment. Safety and tolerability data (see Section 10.4 for definition of safety and tolerability variables) will be summarised by treatment, if applicable.

Frequency counts (number of subjects [n] and percentages) will be made for each qualitative variable. Descriptive statistics (n, mean, standard deviation [SD], median, minimum and maximum) will be calculated for each quantitative variable (unless otherwise stated). Descriptive statistics will only be presented if $n \geq 3$.

The following rules will apply to any repeated safety assessments occurring within each treatment period:

- If the repeated measurement of a specific parameter occurs prior to IMP administration (Day 1), then the last obtained value prior to dosing will be used in the descriptive statistics and in the calculation of changes from baseline;
- If the repeated measurement of a specific parameter occurs after IMP administration (Day 1), then the first (non-missing) value after dosing will be used in descriptive statistics and in the calculation of changes from baseline.

The planned sequence for measurement of multiple assessments at the same time point is described in Section 5.3.5.

For safety assessments performed at Screening and the Follow-up Visit, the following rules will apply for any repeated assessments:

- If the repeated assessment occurs at Screening the last available value will be used in the summary statistics;
- If the repeated assessment occurs at the Follow-up Visit the first non-missing assessment will be used in the summary statistics.

All statistical analyses and production of tables, figures and listings will be performed using SAS[®] version 9.4 or later.

12.2.1. Missing Data

Missing dates and times in the AE data will be handled as described in Section [12.12.2](#). Concentrations that are not quantifiable (NQ) in the PK data will be handled as described in Section [12.10.2](#).

There will be no imputations of other missing data. All subjects will be included into the safety analyses as far as the data permit.

12.3. Study Populations

12.3.1. Randomised Set

The Randomised Set will consist of all subjects randomised into the study.

12.3.2. Safety Analysis Set

The Safety Analysis Set will include all subjects who received at least 1 dose of IMP (verinurad, allopurinol and placebo) and for whom any safety post-dose data are available.

Unless otherwise stated, the Safety Analysis Set will be used for the presentation of all demographic and disposition data, as well as all safety analyses. Exposure to IMP will also be presented using the Safety Analysis Set.

12.3.3. Pharmacodynamic Analysis Set

The PD Analysis Set will consist of all subjects in the Safety Analysis Set for whom baseline and post-baseline QTcF results from smoothed dECG data are available for at least 2 treatment periods (where 1 of the treatment periods needs to be the period in which the subject received placebo) and who have no major protocol deviations thought to impact on the analysis of the dECG data.

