8. STUDY STOPPING RULES

8.1. Discontinuation of Investigational Medicinal Product and Withdrawal from the Study

Subjects must be discontinued from treatment in the following situations:

- Subject decision. The subject is at any time free to discontinue treatment, without prejudice to further treatment.
- Severe noncompliance to study protocol.
- Any significant and clinically relevant changes in the safety parameters (eg, ECG, blood pressure, pulse rate, body temperature, laboratory assessments and AE) making the continuation of IMP administration unjustified.
- Study-specific withdrawal criteria: If a subject reports any event/symptoms that are considered unacceptable by the subject or the Investigator, he/she will be withdrawn from the study. In particular:
 - Any severe or serious AE that is judged as possibly related to the IMP by the Investigator.
 - Any case of Potential Hy's Law (PHL) according to [Appendix C](#).
 - QTc prolongation defined as QTcF >500 ms, or a prolongation from baseline of >60 ms, confirmed (persistent for at least 5 minutes) and determined post-dose either during continuous 12-lead safety ECG monitoring or on a repeat 12-lead safety ECG.
 - See [Appendix D](#) for details on the handling of renal-related or urolithiasis treatment-emergent AEs, and the handling of serum creatinine elevation, which includes criteria for stopping treatment.
 - Pregnancy.
 - Any confirmed COVID-19 case that warrants discontinuation in the judgment of the Investigator or Sponsor to protect the safety of the subject, other study participants or study site staff.

The appropriate AE form in the case report form (CRF) is to be completed.

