9.9.2. Procedures for Randomisation

Upon completion of the randomisation requirements specifications form, randomisation will be produced by Parexel according to the AstraZeneca randomisation system (AZRand).

Subjects will be randomised according to a randomised William's Latin square to receive the 3 study treatments (Treatment A: verinurad 24 mg ER8 + allopurinol; Treatment B: verinurad 40 mg IR + allopurinol, Treatment C: placebo) in 1 of 6 treatment sequences: ABC, BCA, CAB, ACB, BAC, or CBA.

The randomisation will be completed using consecutive randomisation codes.

The number of subject identifiers generated for the study will account for the number of randomised subjects per the sample size calculation (N=24; see Section 12.4) as well as providing sufficient randomisation numbers for replacements. For this study, a total of 48 subject identifiers will be randomly assigned to the treatment sequences (ABC, BCA, CAB, ACB, BAC, CBA).

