12.9. Pharmacodynamic Analysis

Note: In this study, the PD data collected refer to dECG data.

Primary analysis:

A linear mixed-effect concentration-QTcF model will be used as the primary analysis. Baseline-corrected and placebo-adjusted QTcF ($\Delta\Delta\text{QTcF}$), using individual time-matched placebo for a given subject, will be the dependent variable and verinurad plasma concentrations will be the independent variable. Fixed effects will be: intercept in the absence of a treatment effect, slope of the assumed linear association between concentration and $\Delta\Delta\text{QTcF}$ and baseline QTcF. Random effects will be included on the intercept term and the slope. $\Delta\Delta\text{QTcF}$ at the concentration of interest will be estimated. A prolonging effect will be excluded if the upper bound of the two-sided 90% confidence interval for model-derived $\Delta\Delta\text{QTcF}$ is estimated to be <10 ms at the highest clinically

relevant exposure. Details of the concentration-QTcF modeling will be provided in a separate document (C-QT analysis plan).

Relevant exploratory plots will also be provided such as mean change from baseline QTcF vs. drug concentration, QTcF vs. RR and other dECG variables.

Calculations related to the PD variables will be performed by Parexel International. Parexel SOPs and Work Instructions will be used as the default methodology if not otherwise specified.

For dECGs the lead V2 is used as the primary lead, with lead V5 as the primary backup lead and lead II as the secondary backup lead, for all time points when lead V2 is found to be unsuitable for analysis or evaluation. Prior to the statistical analysis and summary, the ECG intervals will be smoothed into target time point values.

After the smoothing of QT and RR into target time point values, the HR-corrected QT will be calculated (QTcF) using the standard formula. All the statistical analyses will be performed using smoothed data.

The QTcF versus RR intervals will be plotted to confirm if HR-correction has been appropriate.

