Digital ECG variables (absolute values and change from baseline for: HR, RR, PR, QRS, QT and QTcF) will be listed by subject and time point and summarised by treatment group using appropriate descriptive statistics (eg, n, geometric mean, arithmetic mean, SD, min, median, max, etc.); in addition, exploratory plots will be provided (such as time course for each dECG variable, changes from baseline for each dECG variable, by treatment group, mean with SD) and time course for $\Delta\Delta$: RR, HR, PR, QRS, QTcF for each treatment group.

The QT and QTcF outliers (defined as values following dosing that are greater than 450 ms or increases from baseline greater than 30 ms) will be summarised using cumulative counts and percentage under the following categories:

- 1 absolute value >450 ms,
- 2 absolute value >480 ms,
- 3 absolute value >500 ms,
- 4 increase from time-matched baseline >30 ms,
- 5 increase from time-matched baseline >60 ms,
- 6 absolute value >450 ms and increase from time-matched baseline >30 ms,
- 7 absolute value >500 ms and increase from time-matched baseline >60 ms.

All PD analyses will be done on the PD Analysis Set. The analysis population of the primary analysis will be defined in the C-QT analysis plan.

Additional analyses of the dECG data will be performed and a corresponding summary table will be presented according to the guidance for the analysis and review of QT/QTc interval data published by Health Canada [23].

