12.12. Analysis of Safety Data

Safety data (scheduled and unscheduled) will be presented in the data listings. Continuous variables will be summarised using descriptive statistics (n, mean, SD, minimum, median, maximum) by treatment. Changes (and/or percentage change) from baseline will be presented where applicable when baseline is defined. Categorical variables will be summarised in frequency tables (frequency and proportion) by treatment. The analysis of the safety variables will be based on the Safety Analysis Set.

Tabulations and listings of data for vital signs and clinical laboratory tests will be presented. Data will be summarised for the observed values at each scheduled assessment, together with the corresponding changes (and/or percentage change) from the baseline when baseline is defined. 12-lead safety ECG data will be listed only. Out-of-range values will be flagged in individual listings for safety laboratory findings, vital signs and 12-lead safety ECGs findings. Furthermore, out-of-range values will be summarised descriptively for safety laboratory findings and vital signs using agreed standard reference ranges and/or extended reference ranges (eg, AstraZeneca, program, or laboratory ranges).

12.12.1. 12-lead Safety Electrocardiogram

The 12-lead safety ECG results will be listed for each subject and out-of-range results will be flagged. Abnormal findings may be classified as AEs if considered clinically significant by the Investigator. See Section 13.2.6 for AE reporting.

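### The QT/QTcF outlier table can omit a subject withdrawn for QTc prolongation on verinurad before the placebo period, although at least its absolute-value categories need no placebo data

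*Combined protocol and SAP*

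**What the plan says.** - **Analysis set.** Section 12.3.3 admits a subject to the PD Analysis Set only with baseline and post-baseline smoothed QTcF in at least two periods, "where 1 of the treatment periods needs to be the period in which the subject received placebo", and without a major deviation affecting the dECG.
- **Where the set is used.** Section 12.9 treats dECG data as the PD data and states: "All PD analyses will be done on the PD Analysis Set". The only exception is the population for the primary analysis, which is left to the C-QT analysis plan.
- **Outlier table.** Section 12.9 lists seven categories. Numbers 1 to 3 are absolute values above 450, 480 and 500 ms. Numbers 4 and 5 are rises above 30 and 60 ms. Numbers 6 and 7 combine the two, the last being "absolute value >500 ms and increase from time-matched baseline >60 ms".
- **Withdrawal rule.** Section 8.1 withdraws a subject from the study for "QTc prolongation defined as QTcF >500 ms, or a prolongation from baseline of >60 ms", once confirmed. The finding is "determined post-dose either during continuous 12-lead safety ECG monitoring or on a repeat 12-lead safety ECG".
- **Data source.** For dECG, Section 12.9 states: "All the statistical analyses will be performed using smoothed data". For the safety ECG, Section 12.12 states: "12-lead safety ECG data will be listed only".
- **Sequences.** Section 9.9.2 randomises subjects "in 1 of 6 treatment sequences: ABC, BCA, CAB, ACB, BAC, or CBA", where C is placebo.

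**The concern.** The placebo condition suits placebo-adjusted ΔΔQTcF. It has no role in a count of absolute QTcF values, and none in a count of change from a pre-dose baseline. Yet the outlier table inherits it.

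The table's 500 ms and 60 ms cut-offs are also those of the withdrawal rule. A subject who meets that rule on verinurad before reaching placebo has no placebo period, fails the set definition, and is left out of the table meant to count such values. Under the assumptions given in the working, the loss is uneven and falls more often on active treatment than on placebo.

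Replacement could make the gap harder to see. Section 7.3 permits it under conditions after a safety withdrawal, and Section 9.9.1 gives the replacement the same sequence. The table could then again show 24 subjects.

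**Working it through.** **The plan's own figure.** Section 12.4 randomises 24 to obtain 20 evaluable, with 17% dropout. (24 − 20)/24 = 4/24 = 16.7%, and 24 × 0.83 = 19.9, so the figure reproduces to rounding. Section 12.4 defines evaluable as Section 12.3.3 defines the PD Analysis Set, so the plan already allows for about 4 subjects outside it.

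**Rule applied.** A subject stopped during a given treatment stays in the set only if the periods up to and including that one number at least two and include C. For this check, the stopping period is taken to have usable baseline and post-dose dECG.

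| Sequence | Stop in period 1 | Stop in period 2 | Stop in period 3 |
|---|---|---|---|
| ABC | A: out | B: out | C: in |
| BCA | B: out | C: in | A: in |
| CAB | C: out | A: in | B: in |
| ACB | A: out | C: in | B: in |
| BAC | B: out | A: out | C: in |
| CBA | C: out | B: in | A: in |

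**Counts**, assuming balanced allocation (24/6 = 4 per sequence):

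- Treatment A is out in ABC, ACB and BAC: 3 × 4 = 12 of 24.
- Treatment B is out in ABC, BCA and BAC: 3 × 4 = 12 of 24.
- Active total: 24 of 48 = 50%.
- Placebo is out in CAB and CBA (only one period): 2 × 4 = 8 of 24 = 33%.
- Ratio: 0.50/0.333 = 1.5. This holds only if a stop is equally likely in every period.

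**By period.**

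- Period 1: 16 of 16 active dosings and 8 of 8 placebo dosings are out.
- Period 2: 8 of 16 active and 0 of 8 placebo.
- Period 3: 0 of 16 active and 0 of 8 placebo.

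All of the imbalance therefore comes from period 2.

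**Effect on the table.** Take one such case, with the other 23 subjects complete and the smoothed dECG confirming the threshold. The table reads 0/23 for that treatment instead of 1/24 = 4.2%. If the subject is replaced and the replacement completes without an outlier, it reads 0/24 instead of 1/25 = 4.0%.

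**Which categories need placebo.** Categories 1 to 3 do not. Categories 4 to 7 depend on *time-matched baseline*, which is not defined. Two places favour the period's own pre-dose value. The outlier definition in Section 12.9 speaks only of increases from baseline, and Table 5-3 schedules a single pre-dose dECG window in each period. So the omission is certain to be unnecessary for a stop above 500 ms. For a stop on the 60 ms rise alone, it is unnecessary on the better-supported reading.

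**The case against.** **The event is still counted elsewhere.** This is the strongest counter-argument, and it largely stands. Section 13.2.6 makes an ECG deterioration an AE when it is the reason for stopping IMP, and Section 8.1 requires the AE form. Section 12.12.2 assigns the AE to the treatment received, tabulates subjects by treatment, and has a category for AEs leading to discontinuation. Section 12.12 bases safety analyses on the Safety Analysis Set. The exclusion itself is listed with its reason (Section 12.6), and the safety ECG is listed. A reader might infer that the case vanishes from the report; the documents do not support that. What is lost is the count by millisecond threshold.

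**Not every category is clearly free of placebo.** This stands in part. The other time-matched quantity in Section 12.9 is the placebo value used for ΔΔQTcF, so categories 4 to 7 are open to a second reading. The claim is firm only for categories 1 to 3.

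**Another table may fill the gap.** Section 12.9 also promises dECG analyses and a summary table following Health Canada guidance. The documents do not give their content. As dECG analyses they appear to fall under the same set, but one can say only that no output stated to use all dosed subjects counts by QTc threshold.

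**The event may never occur.** This is true. Section 5.3.1 reports no indication of QT liability. In Study 101, Section 5.2.1.4 reports four subjects with QTcF above 450 and up to 480 ms, and none above 480 ms. No rate of withdrawal can be derived.

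**One set for all dECG outputs is tidier**, and Section 12.1 permits additional analyses described in the CSR. This is reasonable, but an analysis added after such a case has been seen is weaker than one stated beforehand.

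**Conclusion.** The point holds and is minor. As written, a subject withdrawn for QTc prolongation on verinurad before the placebo period is left out of the QT/QTcF outlier table, without need for categories 1 to 3 and probably without need for categories 4 to 7.

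Given such a stop, exclusion follows in 24 of 48 active dosings (50%) against 8 of 24 placebo dosings (33%). These figures assume 4 subjects per sequence and a stop equally likely in every period.

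Two stronger inferences should be resisted:

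- The 50% is not the share of QTc outliers that the table will miss. It is conditional on a withdrawal. It is also an upper limit on the cases a wider table would recover, because the stop is read on safety ECGs while the table uses smoothed dECG, which may not reach the threshold.
- The primary concentration-QTcF conclusion is not affected. Its population is set in the C-QT analysis plan, and its dependent variable genuinely needs the subject's own placebo values.

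**What to change.** In Section 12.9, for the outlier table only:

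1. Include every Safety Analysis Set subject with at least one post-dose smoothed dECG value in the treatment period concerned, without the two-period and placebo-period conditions.
2. Require that period's pre-dose baseline for categories 4 to 7 only, and replace *time-matched baseline* with the pre-dose baseline of that period.
3. Keep the exclusion for major deviations affecting the dECG.
4. Footnote how many counted subjects lie outside the PD Analysis Set.

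Leave unchanged the PD Analysis Set, the mean Δ and ΔΔ summaries, the primary model and the withdrawal rule. Make the change before unblinding.

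**Cost.** A few sentences and one footnote, with no new data, subjects or models. The drawback is that denominators will differ between treatments and from the PD Analysis Set, and can exceed 24 if a withdrawn subject is replaced. Some counted subjects will have active-treatment data only, so the comparison with placebo in this table is no longer wholly within subject. The footnote discloses this.
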